## **4.4 Product Supply and Accountability**

### Study Product Supply, Distribution and Accountability

Emtricitabine (FTC) 200 mg/tenofovir disoproxil fumarate (TDF) 300 mg study product tablets are manufactured and provided by Gilead Sciences, Inc. under the trade name Truvada®.

### Study Product Acquisition

Emtricitabine (FTC) 200 mg/tenofovir disoproxil fumarate (TDF) 300 mg study product will be supplied by the NIAID Clinical Research Products Management Center (CRPMC). The study site pharmacist can obtain FTC/TDF study products through the CRPMC by following the instructions in the *Pharmacy Guidelines and Instructions for DAIDS Clinical Trial Networks*, and instructions in the SSP Manual.

### Study Product Accountability

The site pharmacist is required to maintain records of all FTC/TDF study products received from the CRPMC and subsequently dispensed to study participants. All unused study products are to be held until the study is completed, terminated, or otherwise instructed by the sponsor. Specific instructions will be provided by the sponsor for return or destruction of the study products.

## **4.5 Toxicity Management**

Guidelines for clinical management and product hold/discontinuation are outlined in this section.

In general, the site investigator has the discretion to hold study product at any time if s/he feels that continued product use would be harmful to the participant, or interfere with treatment

deemed clinically necessary according to the judgment of the investigator. Unless otherwise specified below, the investigator should immediately consult the PSRT for further guidance in restarting study drug or progressing to permanent discontinuation.

#### **4.5.1 Grading System**

The grading system is located in the Division of AIDS Table for Grading Severity of Adult and Pediatric Adverse Events (DAIDS AE Grading Table), Version 1.0, December 2004; Clarification August 2009, which can be found on the Regulatory Support Center (RSC) Web site: <http://rsc.tech-res.com/safetyandpharmacovigilance/>.

#### **4.5.2 Dose Modification**

No dose modifications are permitted.

If absolutely necessary, dosing may be delayed for 2 days in Arms 1-3 during the first 3 weeks on study. Thereafter, all doses in week 4 and 5 must be taken as scheduled. All doses for research participants in Arm 4 must be taken as scheduled. Failure to comply with these schedule requirements will result in termination of the participant from the protocol after a final safety evaluation.

#### **4.5.3 Discontinuation of Study Product in the Presence of Toxicity**

##### **Grade 1 or 2**

In general, participants who develop a Grade 1 or 2 AE regardless of relatedness to study product, and that is not specifically addressed below may continue use of the study product per protocol.

##### **Grade 3**

Participants who develop a Grade 3 AE or toxicity that is not specifically addressed below and is judged to be related to study product should have that study product permanently discontinued. In general, and unless otherwise decided in consultation with the PSRT, the investigator should re-evaluate the participant at least weekly up to 2 weeks to document resolution of toxicity to less than Grade 2.

##### **Grade 4**

Participants who develop a Grade 4 AE or toxicity that is not specifically addressed below regardless of relationship to study product should have the study product permanently discontinued. The participant should be re-evaluated at least weekly up to 2 weeks to show that the adverse event resolves to less than Grade 2.

#### **4.5.4 General Criteria for Discontinuation of Study Product**

Participants may voluntarily discontinue the study products for any reason at any time. Site IoRs will permanently discontinue participants from study product per protocol for any of the specific criteria below, which may be further clarified in the SSP. Site IoRs also may permanently discontinue participants from study product for use of prohibited medication (per Section 4.9), for reasons not shown here or in the SSP (e.g., to protect participants' safety and/or if participants are unable or unwilling to comply with study product use procedures). In such cases, the Site IoRs should first query the PSRT for review. The PSRT will provide a written response to the site indicating whether the PSRT has recommended permanent discontinuation of study product based on careful review of all relevant data.

The criteria for permanent discontinuation of study product use for an individual participant are:

- Study product-related toxicity requiring permanent discontinuation of study product per the guidelines above and below
- Completion of regimen as defined in the protocol
- Request by participant to terminate study product
- Clinical reasons determined by the physician
- Acquires HIV infection, hepatitis B infection
- Becomes pregnant

Any research participant who discontinues participation prematurely for any reason should, prior to discontinuation and dismissal from the study, undergo the safety evaluations regularly scheduled for the final study visit on Day 49, at the time of discontinuation.

### **4.6 Management of Specific Toxicities**

Specific guidance related to permanent discontinuation is also noted here as it pertains to the clinical management of toxicities.

#### **4.6.1 Nausea and Vomiting**

Participants with Grade 1 or 2 nausea or vomiting may be treated symptomatically with hydration, oral antiemetic therapies or antiemetic suppositories at the discretion of the site investigator. Participants should be instructed to take oral study product with food.

Participants with Grade  $\geq 3$  nausea and vomiting for which an alternative etiology is not established must permanently discontinue the study product and be treated symptomatically.

## 4.6.2 Diarrhea

Participants with diarrhea of any toxicity grade may be treated symptomatically with permitted antimotility agents and rehydration at the discretion of the site investigator.

Participants with new onset Grade  $\geq 3$  diarrhea that is unresponsive to antimotility agents and for which an alternative etiology (e.g., infectious diarrhea) is not established must permanently discontinue study product and be treated symptomatically.

## 4.6.3 AST/ALT Elevations

Careful assessments should be done to rule out the use of alcohol, non-study medication-related drug toxicity, or viral hepatitis as the cause of elevation in AST or ALT of any grade. The participant must be carefully assessed for any symptoms or signs of hepatotoxicity, including fatigue, malaise, anorexia and nausea, jaundice, acholic stools, right upper quadrant pain or hepatomegaly. If the AST/ALT elevation is considered most likely to be due to concomitant illness or medication, standard management, including discontinuation of the likely causative agent, should be undertaken. If symptoms or signs of clinical hepatitis are present, study treatment must be discontinued (see below).

### **Grade 1**

For study participants with less than Grade 1 ALT and AST at study entry, an increase to Grade 1 ALT or AST even in an asymptomatic participant may be of concern.

ALT or AST must be repeated as soon as possible (at most within 1 week of the receipt of the results) of a new Grade 1 ALT or AST. Study treatment may be continued while repeating ALT and AST at the discretion of the investigator provided the participant is asymptomatic.

### **Grade 2**

Participants should have ALT or AST re-checked as soon as possible (at most within 1 week) and then be followed weekly until levels are Grade  $\leq 1$ . The frequency of follow up may be altered at the discretion of the site investigator following consultation with the PSRT. Study treatment may continue at the discretion of the investigator provided the participant is asymptomatic.

### **Grade 3/4**

Study product should be permanently discontinued for any ALT or AST of Grade 3 or 4. Participants should have ALT or AST re-checked as soon as possible (at most within 1 week). Participants should then be followed weekly until levels are Grade  $\leq 1$ .

#### **4.6.4 Creatinine Clearance**

If the creatinine clearance is  $<50\text{mL/min}$ , it should be confirmed within 1 week of the receipt of the results in consultation with the PSRT. If the creatinine clearance is confirmed to be  $<50\text{mL/min}$ , the study product must be permanently discontinued. Participants who fail to have a confirmed test will permanently discontinue the study product.

#### **4.6.5 Hypophosphatemia**

##### **Grades 1 and 2.**

The phosphate should be repeated within 1 week of the receipt of the results. Supplemental phosphate should be given with phosphate-rich food or fluid with or without neutral phosphate solution. Other causes of phosphate loss should be thoroughly evaluated.

##### **Grade 3/4**

The phosphate should be repeated within 48 hours of the receipt of the results. Supplemental phosphate should be given with phosphate-rich food or fluid with or without neutral phosphate solution, and other causes of low phosphate should be thoroughly investigated. During the time that supplemental phosphate is provided to the participant and the time that testing is repeated, sites should follow product hold guidelines described in Section 4.5. If alternative etiologies for Hypophosphatemia cannot be identified, the study team will give consideration to discontinuation of study drug. Study medication should be discontinued for resistance to supplemental phosphate intervention after 2 days.

#### **4.6.6 Genital Sexually Transmitted Infection/Reproductive Tract Infection**

Testing for STIs will be performed at screening for all participants. Persons identified as having an STI will be excluded from the intensive cohort and will be referred for management according to the local standard of care. Testing will be performed at other study visits only if the participant develops signs/symptoms of an STI or expresses a concern about having acquired a STI infection after enrollment. If any participant acquires an STI during the study, clinical management will be provided in accordance with current CDC guidelines. Probenecid may not be given with study medications. If probenecid is necessary for STI treatment, the study dosing will be discontinued. Study product need not be held in the event of genital STI/ reproductive tract infection (RTI) requiring treatment, unless other product hold guidelines apply. An STI will result in removal from the study only if treatment is not complete within one week prior to the tissue sampling days in the protocol (intensive sampling cohort only).

#### **4.6.7 HIV and Hepatitis B**

##### HIV Infection

HIV testing will be performed at screening and enrollment. Individuals with one or more reactive HIV rapid test results (regardless of subsequent test results) will be excluded from the study and will be referred for management according to the local standard of care. HIV diagnostic testing will also be performed at the end of the study, and at any other study visit at which a participant has signs/symptoms of acute HIV infection or expresses a concern about having acquired HIV infection after enrollment.

##### Hepatitis B

Hepatitis B testing (HBsAg) will be performed at screening. Persons with a positive HBsAg test will be excluded from the study and will be referred for management according to the local standard of care. Hepatitis B testing will be performed at the end of the study and at other study visits if the participant expresses a concern about having acquired hepatitis B infection after enrollment or as clinically indicated for AST/ALT elevations.

#### **4.6.8 Management of sampling complications**

Tissue and fluids will be obtained in the intensive sampling cohort on Days 35 and 49. All subjects will be required to abstain from sexually activity for 72 hours following sample collection. Subjects will be contacted by phone 24 hours after sample collection to assess for any adverse events.

##### Cervicovaginal Fluid

Collection of CVF requires women to be recumbent for 5 minutes to allow fluid to pool in the posterior fornix. The vaginal sample aspirator is then gently inserted into the vagina without the placement of a speculum. This procedure may cause very slight discomfort, pressure, or irritation that should occur only during the procedure (<5 minutes). Any uncomfortable sensations should resolve shortly after the procedure.

Subjects will not undergo CVF sampling if evidence of vaginitis is present on initial examination.

##### Cervical Cells

Cervical cells will be collected following the insertion of a speculum into the vagina by inserting a cytobrush (two full 360 degree rotations) into the endocervical canal. Minimal discomfort may occur with placement of the speculum. Slight bleeding or spotting may occur after the cytobrush is removed but no more than that which occurs during a normal pap smear.

### Seminal Fluid

Semen will be self-collected in a private room in the research unit. Subjects may experience psychological distress and local irritation or discomfort.

### Vaginal Biopsies

During this procedure subjects may experience some mild pain when the sample is taken. Subjects will receive topical anesthetic prior to the procedure. Bleeding may also occur at the specimen collection site. Bleeding may be stopped at the biopsy site with application of a local anti-coagulant. In very rare cases, a stitch might need to be placed in order to stop bleeding. Under such circumstance, female participants may feel slight soreness or discomfort in the vagina for one to two days after the vaginal biopsy. Participants may experience some vaginal spotting or bleeding and slight discharge for up to one week after the biopsy. In rare instances, a vaginal biopsy may cause infection or prolonged bleeding.

Subjects will not undergo tissue sampling if evidence of vaginitis is present on initial examination.

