### 3.2 Exclusion Criteria

- At screening:
  - Alanine aminotransferase (ALT) or aspartate aminotransferase (AST) greater than 1.5 X the site laboratory ULN (upper limit of normal)
  - Hemoglobin less than 10.0 g/dL
  - Platelet count less than 100,000/mm^3
  - Serum phosphate level below site laboratory LLN (lower limit of normal)
  - INR or aPTT greater than site laboratory ULN
  - Other safety tests (bicarbonate (HCO3), potassium (K), chloride (Cl), sodium (Na), calcium (Ca), fasting glucose) with results outside of the laboratories reference range
  - 1+ or greater protein on urine dipstick testing
  - 1+ or greater glucose on urine dipstick testing
- Culture-confirmed urinary tract infection
- Co-enrollment in any other HIV interventional research study (excluding behavioral only interventions) or prior enrollment in the active arm of a HIV vaccine trial.
- Clinically apparent or patient report of active skin disorders including: rash, pruritus, maculopapular rash, urticaria, vesiculobullous rash, and pustular rash.
- Women who are pregnant or breastfeeding.
- One or more reactive HIV rapid test results at screening or enrollment, even if HIV infection is not confirmed.
- Positive hepatitis B surface antigen (HBsAg) test.
- Excessive use of alcohol (more than 4 drinks a day on a regular basis).
- Interleukin therapy; medications with significant nephrotoxic potential, including but not limited to amphotericin B, aminoglycosides, cidofovir, foscarnet and systemic chemotherapy; and medications that may inhibit or compete for elimination via active renal tubular secretion (including but not limited to probenecid).
- Participants with a history of having a gastrectomy, colostomy, ileostomy, or any other procedure altering the gastrointestinal tract or drug absorption.
- Intensive sampling cohort only:
  - A positive test for syphilis, gonorrhea, or Chlamydia
  - A positive test for HSV-2 (individuals with active lesions only)
  - Findings consistent with bacterial vaginosis, vaginal candidiasis, or trichomonas (women only)
  - History of STI within 3 months prior to enrollment
  - Medications that prolong clotting time (e.g., warfarin, heparin, clopidogrel classes.)
  - Abnormalities of the colorectal mucosa, or significant colorectal symptom(s), which in the opinion of the clinician represents a contraindication to biopsy

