#### **4.9 Concomitant Medications**

With the exception of medications listed as prohibited (see below, this section), enrolled study participants may use concomitant medications during study participation. All concomitant medications, over-the-counter preparations, vitamins and nutritional supplements, recreational drugs, and herbal preparations reported throughout the course of the study will be recorded on CRF designated for that purpose.

All concomitant medications taken or received by participants within the 4 weeks prior to study enrollment will be reported on applicable study CRFs. Medications used for the treatment of AEs that occur during study participation also will be recorded on applicable study case report forms.

Should participants report use of any of the following medications, they will be required to discontinue use of study products and have termination visit evaluations: interleukin therapy; medications with significant nephrotoxic potential, including but not limited to amphotericin B, aminoglycosides, cidofovir, foscarnet and systemic chemotherapy; and medications that may inhibit or compete for elimination via active renal tubular secretion (including but not limited to probenecid).

Medications that prolong clotting time (e.g., warfarin, heparin, clopidogrel classes) are exclusionary as are the conditions they treat. Occasional use of aspirin or non-steroidal anti-inflammatory drugs (NSAIDs) for analgesia is allowed with restriction. Aspirin cannot be taken within 1 week of scheduled biopsies. NSAID cannot be taken within 24 hours of scheduled biopsy. Detailed instructions for preparation for biopsies will be included in the SSP.

Spermicide should not be used by participants who undergo mucosal sampling during the study. Non-study vaginal and rectal products (other than tampons during menstruation, diaphragms and female condoms) are also prohibited for individuals undergoing mucosal sampling. Participants who report current use of these products will be counseled regarding the use of alternative methods. Participants are not expected to require gynecologic surgical procedures during enrollment period; however, should such a procedure be required, the site IoR or designee will consult the PSRT regarding ongoing product use by the participant.

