## **5.9 Participant Preparation for Sampling**

### Preparation and safety evaluations for biopsies

As stated in sections 4.6.8, participants should start a low fiber diet 3 days before each rectal biopsy procedure and have a clear liquid diet 12 hours prior to the procedure. They should also refrain from meals (or coffee) the day of the procedure. Enemas will be administered before the biopsy procedures take place. Additional details on the dietary preparation and enemas will be included in the SSP.

Following enrollment, coagulation testing is done on participants in the intensive sampling cohort at the Day 28 visit. If test results are a Grade 2 or higher, the intensive tissue sampling will be cancelled. If possible, these participants may be transferred into non-intensive sampling cohort if there is an available slot. If a slot is not available, they will be terminated from the study.

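### Section 4.6.8 names an anti-coagulant as the means of stopping bleeding after a vaginal biopsy, a term that contradicts the sentence's own purpose

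*Protocol*

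**What the plan says.** Section 4.6.8 of the Protocol, Management of sampling complications, has a paragraph on vaginal biopsies. On bleeding at the biopsy site it says: "Bleeding may be stopped at the biopsy site with application of a local anti-coagulant". The sentence after it gives a rarer further step: "In very rare cases, a stitch might need to be placed in order to stop bleeding".

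Four other provisions bear on clotting and biopsy:

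- Section 3.2 excludes from the intensive sampling cohort people taking "Medications that prolong clotting time (e.g., warfarin, heparin, clopidogrel classes".
- Section 3.2 also excludes, at screening, "INR or aPTT greater than site laboratory ULN". Table 5-1 assigns coagulation testing at screening to the intensive sampling cohort.
- Section 4.9 states: "Medications that prolong clotting time (e.g., warfarin, heparin, clopidogrel classes) are exclusionary as are the conditions they treat". It then limits analgesics before biopsy: "Aspirin cannot be taken within 1 week of scheduled biopsies", with a 24-hour limit for NSAIDs.
- Section 5.9 requires a coagulation test at Day 28 in the intensive cohort and provides: "If test results are a Grade 2 or higher, the intensive tissue sampling will be cancelled".

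**The concern.** The sentence in section 4.6.8 gives a purpose, stopping bleeding, and a means, an anti-coagulant. By the ordinary meaning of the word, the means opposes the purpose. The paragraph belongs to a section on managing complications, so staff may look there for what to do when a biopsy bleeds. Taken literally, the sentence would make bleeding worse. The stake is the safety of the few women whose biopsy site bleeds enough for an agent to be considered, and the possibility that the wrong term is carried into site documents.

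**Working it through.** The plan gives no figure on this point, so the check is a comparison of the text, followed by a count of who could be affected.

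**1. The sentence against its own purpose.** The purpose is explicit, because the sentence opens with the stopping of bleeding. The next sentence confirms it by giving a stitch for the same end. The two read as successive means to one goal, and only the first names something that acts against that goal. Nowhere in the available protocol text is the term given another meaning or corrected. The vaginal biopsy paragraph in section 8.3 mentions spotting and a small risk of heavier bleeding but names no agent, so it does not settle the matter.

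**2. The sentence against the rest of the protocol.**

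| Place | Subject | How clotting is treated |
|---|---|---|
| 3.2, intensive cohort | Drugs a participant takes | Prolonged clotting time excludes |
| 3.2, at screening | Laboratory values | INR or aPTT above the upper limit excludes |
| 4.9 | Concomitant drugs | Clotting-time drugs exclude; aspirin and NSAIDs are limited before biopsy |
| 5.9, Day 28 | Laboratory values | Grade 2 or higher cancels tissue sampling |
| 4.6.8, Vaginal Biopsies | Product applied locally after biopsy | An anti-coagulant is named as the remedy for bleeding |

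The first four rows point the same way: impaired clotting is something to keep away from the biopsy. The last row points the other way. The first four concern what participants take and what their blood tests show. None addresses a product that a clinician puts on a biopsy site. The mismatch is therefore one of class of agent and rationale, not a literal breach of a rule.

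**3. How many participants.** Inputs: 2 women per arm in the intensive cohort and 4 arms (Schema; section 2.3.2), with vaginal biopsies on Days 35 and 49 (Table 5-4).

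- Women: 2 × 4 = 8 planned, before any replacements under sections 7.3 and 7.4.
- Biopsy visits: 8 × 2 = 16.

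Section 9.2 allows up to 5 biopsies, subject to local IRB limits, and does not say whether that is per visit or per woman. The ceiling is 8 × 5 = 40 biopsies on one reading and 16 × 5 = 80 on the other. Neither is the number affected. The sentence applies only where a site bleeds and an agent is used, and the protocol gives no bleeding rate. All that can be said is that between 0 and 16 planned visits are affected.

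**The case against.** The strongest reply is that the intended meaning is plain on the page. The sentence begins with stopping bleeding, a stitch follows for the same end, and the surrounding rules all guard against poor clotting. A trained clinician would very likely see a slip of the pen. The paragraph is also largely descriptive, saying what may happen and what may be done, with no product, amount or step. Section 5.0 leaves detailed procedural instructions to the SSP manual, which is not at hand and may already be right. All of this stands, and it limits the severity. It does not make the sentence correct.

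A reader might infer three stronger points that the documents do not support.

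- **That section 4.6.8 breaches the exclusions in 3.2 and 4.9.** Those govern eligibility and participants' own medications, and they name drugs that prolong clotting time, including the clopidogrel class, not locally applied products. Section 4.9 does not give biopsy as the reason for the clotting-drug exclusion. That link is a reasonable inference from the cohort-only placement in 3.2 and from the aspirin and NSAID limits.
- **That safety is at risk at every vaginal biopsy.** The sentence matters only after bleeding has occurred.
- **That the study's data or power are threatened.** Section 4.6.8 stops further tissue sampling after excessive bleeding, but section 7.3 provides for replacement of inevaluable intensive-cohort participants. Nothing in the protocol ties this wording to any expected loss.

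**Conclusion.** The point holds as a wording error in a complication-management section. The term used in 4.6.8 is opposite in action to the purpose stated in the same sentence, and it is out of line with how sections 3.2, 4.9 and 5.9 treat impaired clotting. The contradiction inside the sentence is enough by itself; the other sections are supporting context. The conclusion assumes only that the word carries its ordinary meaning, since the protocol gives no other. It is most likely a slip. Its reach is the bleeding biopsies among 8 planned women over 16 planned visits, a number the documents do not allow one to estimate. Sample size, power and the planned analyses are unaffected. Severity: minor.

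**What to change.** The protocol's clinical team should reconcile the term in the vaginal biopsy paragraph of 4.6.8 with the purpose stated there and with sections 3.2, 4.9 and 5.9. They should state what class of agent was meant; that is their decision, and none is suggested here. A clarification memo, issued before site procedures or training rely on the sentence, would do. The SSP manual should be checked for the same term at that time. The cost is a correction of about one word and the memo that carries it, with no change to design, sample size or analysis.
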